#### **8.4 Safety Analyses**

Adverse events will be coded using the Medical Dictionary for Drug Regulatory Activities (MedDRA). Ocular and systemic treatment emergent adverse events (TEAEs) will be summarized by primary system organ class and preferred term. Actual values and change from baseline values for vital signs, clinical laboratory (hematology and chemistry) tests and other continuous variables (both ocular and non-ocular) will be summarized with descriptive statistics. Concomitant medications, physical examinations, and other categorical (safety) variables (both ocular and non-ocular) will be summarized with frequency and percentage distribution. All safety analyses will be performed using the Safety Analysis Set.

#### **8.5 Pharmacokinetics Analyses**

Individual and mean serum NGM621 concentration–time data will be tabulated and plotted by cohort/dose level.

CCI

Additional PK analyses and/or summary statistics will be conducted as appropriate. All PK analyses will be performed using the PK Analysis Set.

#### **8.6 Sample Size Determination**

Subjects will be randomized in a 2:1:2:1 ratio to receive treatment with NGM621 Q4W, Sham Q4W, NGM621 Q8W, or Sham Q8W. Subjects from the two Sham groups will be pooled in the data analysis.

A sample size of 106 subjects per treatment group (i.e., 318 subjects in total) is expected to provide approximately 90% (NGM621 Q4W vs pooled Sham) and 85% (NGM621 Q8W vs pooled Sham) power to detect a statistically significant treatment group difference in the rate of change in GA lesion area over the 52 weeks of treatment. The power is estimated based on simulations assuming a mean GA lesion area of 8 mm^2 at baseline for all subjects, a common standard deviation of 4 mm^2 for GA lesion area, a linear slope of 2 mm^2 per year for the

pooled Sham group, 1.4 mm^2 per year for NGM 621 Q4W and 1.45 mm^2 per year for NGM 621 Q8W, a within-subject correlation of 0.95, a statistical significance level of 5% (two-sided), and a 10% of subject dropout rate. These assumptions are based on published data

CCI

CCI

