### **3 Study Objectives and Endpoints**

#### **3.1 Primary Objectives and Endpoints**

The primary objectives of this study are to evaluate the efficacy and safety of NGM621 intravitreal (IVT) injections administered every 4 or 8 weeks for a total of 52 weeks.

- The primary efficacy endpoint is the rate of change in GA lesion area as measured by fundus autofluorescence (FAF) over the 52 weeks of treatment.
- The primary safety endpoints will evaluate the incidence and severity of ocular and systemic adverse events from treatment with NGM621 administered every 4 or 8 weeks compared to Sham.

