## 4 Study Design

### 4.1 Methodology/ Study Design:

This is a Phase 2 randomized, double-masked, Sham-controlled, multicenter study of the safety and efficacy of IVT injections of NGM621 in subjects with GA secondary to AMD in one or both eyes. Only one eye can be chosen as the study eye. In the event both eyes are eligible, the eye with the worse visual function (lower BCVA value) will be considered for the purpose of this study as the study eye. If both eyes have the same visual function, the eye with the larger area of GA will be selected as the study eye. In the event that both eyes have the same visual function and GA area, the right eye will be selected.

Approximately 318 subjects, screened within 4 weeks prior to dosing, who have signed the informed consent and meet all eligibility criteria, will be assigned randomly to 1 of 4 treatment groups in a ratio of 2:1:2:1 to receive IVT injections of 15 mg of NGM621 (100  $\mu$ L volume) or Sham, every 4 weeks or every 8 weeks for a total of 52 weeks ([Table 2](#)). Subjects will be monitored for 56 weeks, and the total duration of individual participation (including screening time) will be approximately 60 weeks. Subjects who discontinue before completion of 52 weeks of treatment may be replaced. Mesopic microperimetry of the study eye only will be performed at select study sites. For additional details please refer to [Section 7.3.14.5](#).

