## 8 Statistical Considerations

A detailed statistical analysis plan (SAP) will be provided and finalized prior to the study database lock or unmasking. No discrepancies are expected between the SAP and the protocol. However, if there are discrepancies between this section of the protocol and the final SAP, the SAP will override the protocol.

In general, descriptive statistics including the number of non-missing observations (n), arithmetic mean (mean), standard deviation (SD), median, minimum (min), and maximum (max) will be presented by treatment group for continuous endpoints. Frequency and percentage distribution will be presented by treatment group for categorical endpoints.

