### 8.1 Analysis Sets

Subjects will be analyzed using the following analysis sets:

- Modified Intent-To-Treat (mITT) Analysis Set: All randomized and treated (with at least one dose of study drug) subjects. This analysis set will be used for all efficacy analyses and subjects will be analyzed based on the treatment group into which they are randomized.
- Per Protocol (PP) Analysis Set: a subset of subjects in the mITT Analysis Set who have no protocol deviations that affect the GA lesion assessments (by FAF). This analysis set will be used for sensitivity analyses to support the mITT analyses.
- Safety Analysis Set: All treated subjects. This analysis set will be used for all safety analyses and subjects will be analyzed based on the actual treatment they receive.
- Pharmacokinetic (PK) Analysis Set: a subset of subjects in the Safety Analysis Set who have quantifiable PK measurements post first dose. This analysis set will be used for all PK analyses and subjects will be analyzed based on the actual treatment they receive.

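### Does the open-ended rule for pooling the two Sham groups distort the safety comparison?

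*Combined protocol and SAP*

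**What the plan says.** The pooling rule, "Subjects from the two Sham groups will be pooled in the data analysis", stands in Section 8.6 (Sample Size Determination), directly before the power statement. The same section counts three groups: "A sample size of 106 subjects per treatment group (i.e., 318 subjects in total", that is, NGM621 Q4W, NGM621 Q8W and pooled Sham. Section 4.1 counts four; subjects "will be assigned randomly to 1 of 4 treatment groups in a ratio of 2:1:2:1", and Table 2 lists 106, 53, 106 and 53.

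Pooled Sham is named as the comparator in the primary estimand (8.3.1.1), the main estimation (8.3.1.2) and the secondary efficacy analysis (8.3.2). Section 8.4 on safety names no comparator column: "Ocular and systemic treatment emergent adverse events (TEAEs) will be summarized by primary system organ class and preferred term". Section 8 adds "Frequency and percentage distribution will be presented by treatment group for categorical endpoints" without saying which count of groups applies. For the Safety Analysis Set, Section 8.1 says "This analysis set will be used for all safety analyses and subjects will be analyzed based on the actual treatment they receive".

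Section 3.1 makes the "incidence and severity of ocular and systemic adverse events from treatment with NGM621 administered every 4 or 8 weeks compared to Sham" a primary safety endpoint. Section 8 also states that "if there are discrepancies between this section of the protocol and the final SAP, the SAP will override the protocol".

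**The concern.** Taken literally, the pooling sentence covers every analysis, safety included. The two Sham groups are not examined equally often, because the Q8W arms have telephone contacts instead of visits at Weeks 12, 20, 28, 36 and 44. Section 7.4.1.5 defines iritis and vitritis by inflammatory cells, which are seen on examination, so a brief case without symptoms can be missed by telephone.

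With no drug effect at all, NGM621 Q4W would then tend to show slightly more such findings than pooled Sham, and NGM621 Q8W slightly fewer. The second error favours the drug, in the regimen that Section 2.4 presents as the lighter burden. Section 6.2.1.2 gives each regimen Sham subjects on the same assessment schedule, so the mismatch looks avoidable at no cost.

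**Working it through.** **1. What the 106-per-group count belongs to.** Section 8.6 gives SD 4 mm², within-subject correlation 0.95, slope differences 2 − 1.4 = 0.60 and 2 − 1.45 = 0.55 mm²/year, and 10% dropout. Residual variance = 16 × (1 − 0.95) = 0.8. FAF at 0, 24/52 and 1 year gives a sum of squares for time of 0.501, so the slope SD = √(0.8/0.501) = 1.264. With 106 × 0.9 = 95.4 per group and two-sided 5%, power is 90.7% and 85.2%, against about 90% and 85% stated. The three-group count is therefore the efficacy calculation with pooled Sham as one group. FAF timing is the same in all arms, so pooling does no harm there.

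**2. Exam counts (Sections 7.2.3 to 7.2.17).** Post-baseline slit-lamp and fundus exams:

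- Q4W: Weeks 1, 4, 8, then every 4 weeks to 56 = 15.
- Q8W: Weeks 1, 4, 8, 16, 24, 32, 40, 48, 52, 56 = 10.
- Pooled Sham: (53 × 15 + 53 × 10)/106 = 12.5. Ratios: 15/12.5 = 1.20 and 10/12.5 = 0.80.

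Adverse event contacts are 15 in each schedule (10 visits + 5 calls in Q8W), and the SD-OCT weeks in Section 7.2 coincide. The mismatch concerns only silent findings that need an exam.

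**3. Size of the tilt.** The documents give no usable incidence, so all incidences here are assumed. Model: no drug effect, constant onset rate over 56 weeks, fixed duration D. A finding is recorded if an exam falls within its duration. Detectable onset weeks (Q4W / Q8W) are 29/19 for D = 2, 56/36 for D = 4, 56/46 for D = 6 and 56/56 for D = 8. With true incidence I, recorded incidence = 1 − (1 − I)^(weeks/56), and gap = (Q4W − Q8W)/2.

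Example, I = 5%, D = 4: Q4W 5.00%; Q8W 1 − 0.95^(36/56) = 3.24%; gap = 0.88 points, or 0.0088 × 106 = 0.93 subjects.

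| Assumed I | D = 2 | D = 4 | D = 6 | D ≥ 8 | 95% half-width, 106 v 106 |
|---|---|---|---|---|---|
| 1% | 0.09 | 0.18 | 0.09 | 0 | 2.7 |
| 2% | 0.18 | 0.35 | 0.18 | 0 | 3.8 |
| 5% | 0.45 | 0.88 | 0.44 | 0 | 5.9 |
| 10% | 0.90 | 1.73 | 0.85 | 0 | 8.1 |
| 20% | 1.81 | 3.32 | 1.63 | 0 | 10.8 |

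Gaps and half-widths are in percentage points; half-width = 1.96 × √(I(1 − I) × 2/106). The sign is plus for Q4W and minus for Q8W.

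A cruder model, with the same chance of a finding at every exam, gives a larger tilt. At 1% per exam, recorded incidence is 14.0% in Q4W, 9.6% in Q8W and 11.8% in pooled Sham, a gap of 2.2 points. From 0.1% to 2% per exam the gap runs from 0.25 to 3.9 points, which is 0.15 to 0.67 standard errors of the Q4W contrast.

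**4. Would matched Sham alone be better?** The standard error grows by √(1/106 + 1/53)/√(2/106) = 1.22. Total error counts bias and noise together. For pooled Sham it is √(gap² + p(1 − p)/106 + s(1 − s)/106), with p the recorded incidence in the NGM621 arm and s that in pooled Sham. For matched Sham it is √(p(1 − p)(1/106 + 1/53)).

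Example, Q4W, I = 5%, D = 4, s = 4.12%: pooled √(0.0000774 + 0.000448 + 0.000373) = 3.0 points; matched √(0.0475 × 0.0283) = 3.7 points. For Q8W: 2.7 pooled, 3.0 matched.

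Over four durations, five incidences and two regimens (40 cells), matched Sham has the larger error in 39. The exception is Q8W, D = 4, I = 20%: 5.7 matched against 5.9 pooled.

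**The case for a change.** The strongest case is that direction matters more than size. A primary safety endpoint should have a named comparator, and a known tilt towards the less frequent regimen should not be left in place when matched Sham subjects exist. The literal wording supports this reading. Efficacy already names pooled Sham elsewhere, so the unrestricted sentence seems to add something, and the three masked labels for the DSMB (A, B, C) in Section 4.3 fit a pooled column. Scheduled procedures differ too. By visit headings there are 13 in Q4W, 7 in Q8W and 10 on average in pooled Sham, so procedure-related events are also mismatched.

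Part of this stands. The exam and procedure counts are right, the term treatment group is used in two senses, and the text does not settle the safety columns. But Section 4.3 concerns monitoring outputs, not final tables. Section 8 gives precedence to a separate SAP, whose table specification is not in the text available. Section 8.4 plans descriptive summaries only, so no safety test is distorted. The difference in procedures follows from the regimens and is known for every subject; separate Sham columns would show it without any change to the design or the data collected.

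The Phase 1 result of 0 cases of ocular inflammation in 15 subjects over 12 weeks does not bound the incidence. Its 95% upper limit is 1 − 0.05^(1/15) = 18.1%, which at a constant rate is 1 − (1 − 0.181)^(56/12) = 61% over 56 weeks. The incidence range above is therefore an assumption throughout.

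A separate matter is that Section 7.2.12 is titled a treatment visit and lists post-dose checks at Week 36 but has no dosing line. Those entries must be reconciled. The exam counts do not depend on them; the 13 procedures do (12, and 9.5 in pooled Sham, if Week 36 is not counted).

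**Conclusion.** No change to the plan is called for. The documents do not say that safety tables pool Sham, and four-arm tables are at least as natural a reading of Sections 4.1, 8 and 8.4. If Sham were pooled, the persistence model puts the tilt below one percentage point, and below one subject in 106, at 5% incidence or less. It reaches 3.3 points only at an assumed 20% incidence with findings lasting 4 weeks. It disappears at 8 weeks and stays inside sampling error throughout. Replacing pooled Sham by the matched arm trades this small bias for more noise and nearly always loses.

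Naming the safety columns is table specification that analysts can supply from the randomised arms, for instance by showing both Sham schedules beside the pooled column. Efficacy power is untouched. The conclusion rests on assumed incidences, no drug effect, constant onset and silent findings. A much higher rate of silent findings lasting about 4 weeks would make separate Sham columns more informative, and they could still be produced from the same data.

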### ***Main Estimation***

The GA lesion area (at baseline, Week 24, and Week 52) will be analyzed using a random coefficients model. The model includes terms for time (continuous variable assuming linearity) and treatment-by-time interaction. The intercept and slope of time are assumed to be random effects with a bivariate normal distribution and an unstructured (UN) covariance matrix while the treatment-by-time interaction is assumed to be a fixed effect. If there is a convergence issue under the assumed covariance structure (UN) for the random effect, then a variance-components covariance structure will be used. The within-subject errors are assumed to be independent and identically distributed normal random variables and are assumed to be independent of the random intercept and random slope. Within the framework of this model, a point estimate of the treatment group difference in the regression slope between each NGM621 group and the pooled Sham group will be provided. The corresponding two-sided 95% confidence interval and p-value for the point estimate will also be presented.

A hierarchical testing procedure will be used to control the family-wise type-I error rate associated with the tests of the two NGM621 groups (NGM621 Q4W vs pooled Sham and NGM621 Q8W vs pooled Sham). Specifically, the comparison between NGM621 Q4W and pooled Sham will be performed first. If this test is statistically significant at the 5% level, then the comparison between NGM621 Q8W and pooled Sham will be performed. If the first test is not statistically significant at the 5% level, then the comparison between NGM621 Q8W and pooled Sham will be considered exploratory.

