#### 8.3.1.2 Main Estimation

The GA lesion area (at baseline, Week 24, and Week 52) will be analyzed using a random coefficients model. The model includes terms for time (continuous variable assuming linearity) and treatment-by-time interaction. The intercept and slope of time are assumed to

be random effects with a bivariate normal distribution and an unstructured (UN) covariance matrix while the treatment-by-time interaction is assumed to be a fixed effect. CCI

Within the framework

of this model, a point estimate of the treatment group difference in the regression slope between each NGM621 group and the pooled Sham group will be provided.

[figure not shown]
The corresponding two-sided 95% confidence interval and p-value for the point estimate will also be presented.

A hierarchical testing procedure will be used to control the family-wise type-I error rate associated with the tests of the two NGM621 groups (NGM621 Q4W vs pooled Sham and NGM621 Q8W vs pooled Sham). Specifically, the comparison between NGM621 Q4W and pooled Sham will be performed first. If this test is statistically significant at the 5% level, then the comparison between NGM621 Q8W and pooled Sham will be performed. If the first test is not statistically significant at the 5% level, then the comparison between NGM621 Q8W and pooled Sham will be considered exploratory.

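### The 85% power stated for NGM621 Q8W leaves out the hierarchical gate; on the plan's own assumptions the chance of a confirmatory Q8W result is about 80%

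*Combined protocol and SAP*

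**What the plan says.** Section 8.6 (Sample Size Determination) plans 106 subjects in each comparison group, 318 overall. For the primary endpoint, the slope of lesion area over the year, it credits this size with "approximately 90% (NGM621 Q4W vs pooled Sham) and 85% (NGM621 Q8W vs pooled Sham) power to detect a statistically significant treatment group difference". It also notes that "Subjects from the two Sham groups will be pooled in the data analysis", so the comparison is between three groups of equal size. The power is said to come from simulation at a two-sided 5% level.

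Section 8.3.1.2 (Main Estimation), repeated in the Synopsis, sets the testing rule. "Specifically, the comparison between NGM621 Q4W and pooled Sham will be performed first". If that test is significant at 5%, Q8W is tested next, also at 5%. If it is not, "the comparison between NGM621 Q8W and pooled Sham will be considered exploratory".

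The Protocol Change History shows that the same amendment raised the sample size from 240 to 318 and replaced the Hochberg procedure with this hierarchical sequence. The visible text of Section 8.6 does not mention the sequence, gives no joint power, and does not describe the 85% as applying to Q8W tested alone.

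**The concern.** Under a fixed sequence, the first hypothesis keeps its stand-alone power. The second can be claimed only when the first has also been rejected, so its power is the probability that both tests are significant, which cannot exceed the stand-alone figure. If 85% is the probability that Q8W would be significant when tested by itself, it overstates the chance that the trial delivers a confirmatory Q8W result.

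The figure matters because Q8W against pooled Sham is one of the two primary comparisons. Section 2.4 presents Q8W as the less burdensome regimen and says that the two intervals are meant to inform the dosing frequency in later studies. The amendment enlarged the trial in order to secure adequate power, so the stated power should be the power of the testing procedure adopted with it.

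**Working it through.** **Inputs, all from Section 8.6**

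- 106 subjects per group (Q4W, Q8W, pooled Sham), with 10% dropout: 106 × 0.9 = 95.4 evaluable per group.
- SD of lesion area 4 mm², within-subject correlation 0.95.
- Slopes: Sham 2 mm²/year, and "1.4 mm 2 per year for NGM 621 Q4W and 1.45 mm 2 per year for NGM 621 Q8W". The differences from Sham are 0.60 and 0.55 mm²/year.
- Two-sided 5% significance level (critical value 1.96).

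**Step 1. Reproduce the stated powers**

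The one-year change from baseline serves as a simple stand-in for the slope.

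- SD of change = 4 × √(2 × (1 − 0.95)) = 4 × √0.10 = 1.265 mm².
- SE of a group difference = 1.265 × √(2 / 95.4) = 0.183.
- Q4W: 0.60 / 0.1831 = 3.276; 3.276 − 1.960 = 1.316; power = Φ(1.316) = 90.6% (stated 90%).
- Q8W: 0.55 / 0.1831 = 3.003; 3.003 − 1.960 = 1.043; power = Φ(1.043) = 85.2% (stated 85%).

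Without dropout the same formula gives 93.2% and 88.6%, which do not match. The printed figures therefore correspond to each comparison tested alone at 5%, with 10% dropout.

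**Step 2. Apply the gate**

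Both comparisons use the same pooled Sham group and all three groups are the same size. The covariance of the two differences is the variance of the Sham mean, σ²/n, and each difference has variance 2σ²/n, so the correlation is 0.5.

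- P(both significant) = Φ₂(1.316, 1.043; ρ = 0.5) = 79.8%.
- Starting instead from exactly 90% and 85%: Φ₂(1.282, 1.036; ρ = 0.5) = 79.3%.
- Q8W nominally significant but blocked by the gate: 85.2% − 79.8% = about 5% of trials.

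**Step 3. Check against other ways of doing the calculation**

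| Approach | Q4W alone | Q8W alone | Both (confirmatory Q8W) |
|---|---|---|---|
| Normal theory, one-year change, 10% dropout | 90.6% | 85.2% | 79.8% |
| Simulation, one-year change in completers (200,000 runs) | 90.6% | 85.1% | 79.8% |
| Slope model with common intercept, visits at 0, 24 and 52 weeks, dropouts contributing baseline only | 91.3% | 86.1% | 81.0% |
| Same slope model, all dropouts contributing Week 24 | 91.9% | 86.8% | 82.1% |
| Normal theory, no dropout | 93.2% | 88.6% | 84.5% |

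The common intercept follows Section 8.3.1.2, whose model has terms for time and treatment-by-time but no treatment main effect. In every row the gate takes 4 to 5 points off the stand-alone Q8W power. The only row that approaches 85% after the gate assumes no dropout, and its stand-alone powers are not the printed ones.

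**The case against.** The strongest reply is that nothing has been miscalculated. Section 8.6 attaches each power to a named comparison at a stated 5% level, which is a legitimate per-comparison power and reproduces as such. The gate is set out openly in Section 8.3.1.2, so an attentive reader can see that a Q8W claim depends on Q4W. This much stands: the arithmetic behind 85% is sound, and labelling it as stand-alone power would be an acceptable correction. The sentence as printed has no such label, and it is offered as the power of a design whose procedure does not test Q8W on its own.

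Three further points deserve weight.

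- Part of Section 8.6 after the reference to published data is redacted, and a remark on the gate could sit there. That cannot be excluded, so the statement about absence covers the visible text only. The visible 85% still matches the ungated test and not the gated one.
- The 79.8% comes from a change-score approximation, while the planned slope model gives 81% to 82%. That is correct, but the same model gives stand-alone powers of 91% to 92% and 86% to 87%. The joint figure that goes with the printed 90% and 85% is 79.3%. The sponsor's own simulation would settle the last point or two.
- The consequences are limited. Family-wise error control holds, Q8W is tested at the full 5% when reached, and its estimate and confidence interval are reported even if the gate closes. All of this is true, and it limits the matter to the accuracy of a stated design property.

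**Conclusion.** The concern holds. The stated 85% is the power of Q8W tested alone. Under the hierarchical procedure the probability of a confirmatory Q8W result is about 80%, so the type II error is about 20% rather than 15%. The Q4W figure of 90% is right as it stands, because Q4W is tested first at the full 5%.

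The result rests on the planning assumptions in Section 8.6, on equal group sizes (which give the correlation of 0.5), and on normal approximations. The timing of dropout and the use of Week 24 data in the sponsor's simulation are not given. The variants tried with 10% dropout and that correlation run from 79% to 82%, so the conclusion does not depend on those details.

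**What to change.** In Section 8.6, restate the Q8W power as about 80% under the hierarchical testing procedure, with Q4W at about 90%. The exact gated figure is best taken from the sponsor's existing simulation, by counting the runs in which both comparisons are significant. If the 85% is kept, label it as the stand-alone power that ignores the gate, preferably with the gated figure beside it.

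The cost is one sentence and a Q8W figure about 5 points less favourable. Sample size, testing order and analysis stay as they are. For scale only: holding 85% for Q8W after the gate would take about 120 per group (360 in total) by the change-score approximation. The correction does not call for that increase.
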